5. STUDY MODALITIES

5.1 FWGE

- 5.11 Formulation: American BioSciences Inc, who is the exclusive manufacturer of FWGE in the Unites States, produces fermented wheat germ extract. See Letter of Support (Appendix II). It is formulated as a granulate. One package contains 5.53 grams of FWGE combined with natural orange flavor and stevia Reb-A sweetener to create an instant drink mix. See compositional analysis (Appendix III).
- 5.12 Administration: FWGE is dissolved in 150ml water and taken orally daily.
- 5.13 Adverse effects

The clinical safety experience of FWGE is derived from trials in which FWGE has been used as a single agent or in combination with chemotherapeutic agents. FWGE has not been associated with any grade 3 or 4 toxicities

- 5.14 Storage: FWGE is to be maintained at <80 degrees F
- 5.15 Quality assurance of the manufacturing of FWGE in the U.S.
 - 5.151 The purchased wheat germ and yeast, which are the raw materials of FWGE production, are certified for human consumption. The origin of the wheat germ and yeast, used in the fermentation, are all U.S. certified.

- 5.152 After each batch of FWGE has been freeze-dried, it is tested for hazardous contaminates, such as toxic elements, including heavy metals, and for toxic microorganisms, such as E.Coli, Listeria, etc. Once, the lyophilizate has been found free from toxic contaminants, and has been qualified as microbiologically safe (such as complete lack of toxic micriorganisms, etc.), it is standardized to ensure batch-to-batch chemical compositional homogeneity and biological efficacy-related reproducibility.
- 5.153 For this purpose, a characteristic high performance liquid chromatography (HPLC) fingerprint UV chromatogram of FWGE is compared with the HPLC fingerprint UV chromatogram of an established standard marker "core" of FWGE (reference pattern). As a result of a 2-years research collaboration between the manufacturer and an NCI-designated Cancer Center in the U.S., the marker "core" of the FWGE has been developed and validated to possess the characteristic biological effects of FWGE, including testing by *in vitro* antiproliferative assays using human cancer cell lines; kinase panel tests; robust gene expression assays by quantitative proteomic analysis, using isobaric tag for relative and absolute quantitation labeling technique with electrospray mass spectrometry; and by laboratory animal cancer experiments. The said reference pattern of the standard marker "core" of FWGE has been established to comprise peaks characterized by retention times and relative retention quotients, respectively.

The said fingerprint of the representative sample of the FWGE batch must be identical with the reference pattern. (Chemical standardization/Qualitative chemical assay.)

- 5.154 The quality of the marker "core" in each FWGE batches must also meet a fixed reference value. (Chemical standardization/Quantitiative chemical assay.)
- 5.155 FWGE batches are also characterized by quantitative biological assays according to *in vitro* anticancer protocols. Each and all batches must show the required quantitative biological efficacy. (biological standardization.)

5.2 Placebo

5.21 Formulations: American BioSciences Inc, who is the exclusive manufacturer of FWGE in the Unites States, produces the placebo. See Letter of Support (Appendix II). It is formulated as a granulate. One package contains cooked,

dried and pulverized, white and black rice, 5.53 grams, combined with natural orange flavor and stevia Reb-A sweetener, to create an instant drink mix. See compositional analysis placebo (Appendix IV).

5.22 Administration: FWGE Placebo is a dissolved in 150ml water and taken orally daily.

5.23 Supplier: American BioSciences Inc

5.24 Storage: to be maintained at <80 degrees F

5.3 Drug Accountability: The investigator, or a responsible party designated by the investigator, will maintain a careful record of the receipt, disposition, and return of all drugs received from American Biosciences Inc.

5.4 Drug Dispensing: FWGE and placebo will be in unidentified packages. A random number table will be used to assign patients to the FWGE versus placebo group. The key will be held by the investigational pharmacy and is not revealed to the researchers or patients until the study is complete.

5.4 Unblinding: This is a double-blind study. The treating physician and/or patient may be informed as to which regimen the patient was assigned if either of two situations arises: serious adverse reaction occurs or study completion. In the case of an adverse reaction, the treating physician must contact the Study Chair to obtain permission to break the blind. The Study Chair will notify the Pharmacy which in turn will notify the treating physician. The patient will be considered off study treatment at that time.

6. TREATMENT PLAN AND ENTRY PROCEDURE

Prior to enrollment, approval will be obtained from the scientific review committee and the institutional review board.

6.1 Patient Entry and Registration

6.11 An informed consent and personal health information release will be signed by each patient enrolled.

6.12 All eligibility requirements indicated in Section 4.0 must be satisfied.

6.2 Treatment plan

- 6.21 All subjects will undergo:
 - 6.211 history and physical examination within 28 days of study entry.
 - 6.212 laboratory evaluation: complete blood count, differential, comprehensive metabolic panel and CA125 test prior to starting protocol therapy and preoperatively.
 - 6.213 serum pregnancy test (within 7 days of starting study drug), for women of child-bearing potential.
 - 6.214 Evaluation for National Cancer Institute's Common Toxicity Criteria, all grades at the time of enrollment, then weekly and the day of surgery.
 - 6.215 Quality of life questionnaire (FACT-O) at the time of enrollment, then weekly and the day of surgery (Appendix I).
- 6.22 Patients will be randomized to treatment with either FWGE or placebo and assigned a blinded treatment number corresponding to one of the two treatment groups. The pharmacy will label the appropriate blinded drug specifically for the patient. A daily supply of drug will be given to the patient from the study pharmacy. The amount will be determined by the time until the surgical procedure is scheduled. Neither patients nor treating physicians will be informed of patients "treated/control" status.

Participants will undergo their planned surgery within 4th week after entry into the study. However, if there are delays, patients can continue to take drug/placebo

for a time period no greater than 2 months. If surgery has not occurred after this 2-month period, the patient will be removed from the study.

Participants will take the study drug up until the day prior to surgery. A separate consent form will be obtained for the surgical procedure.

6.23 The primary tumor tissue obtained during the subject's surgery will be transferred to the pathology department for processing.

6.231 Formalin Fixation

Tissue will undergo formalin fixation then embedment in paraffin; tumor tissue will be stained using the H&E process and will be examined by light microscopy. The tumor will also be stained by immunohistochemical (IHC) stain for proliferation marker Ki-67 (Anti-Ki67 primary antibody, catalog number 790-2910, Ventana, Tucson, AZ, USA). The proliferation index will be calculated by percent of nuclear staining of the tumor for tumor tissue treated with FWGE versus placebo and the result will be compared. The reading pathologist will be blinded to the treatment group.

6.232 Fresh frozen

An additional specimen, approximately 30mg, will be flash frozen.

6.233 RNA extraction and Affymetrix gene expression analysis
A total of 20 fresh frozen primary OVCA tissues (10 FWGE- and 10 placebo-treated) will be used for RNA extraction. Tissues (~30mg) will be submerged in lysis buffer. Tissues are then pulverized in BioPulverizer H tubes (Bio101) using a Mini-Beadbeater (Biospec Products). Tubes are spun briefly to pellet the garnet mixture and reduce foam. The lysates are then transferred to a new 1.5 ml tube using a syringe and 21 gauge needle, followed by passage through the needle 10 times to shear genomic DNA. Total RNA will be collected using the Qiagen RNeasy Mini kit according to the manufacturer's instructions. RNA quality will be checked on an Agilent Bioanalyzer to assess quality of RNA via the 28S:18S ribosomal RNAs.

Microarray analysis: 10 μ g of total RNA will be used to develop the targets for Affymetrix microarray analysis and probes will be prepared according to the manufacturer's instructions. Briefly, biotin-labeled cRNA is produced by in vitro transcription, fragmented, and hybridized to customized Human Affymetrix U133-Plus 2.0 gene chip arrays at 45° C for 16 hours and then washed and stained using the GeneChip Fluidics.

Method of statistical analysis: The expression value will be calculated and normalized using iterative rank-order normalization (IRON) [18]. IRON has been shown to perform better than both MAS5 and RMA and is not model based like RMA. Batch effects will be checked by using PCA; if present, they will be removed using COMBAT [19]. The 54,675 probesets will be screened to remove control probesets, probesets with a small variance, and probesets expressed at low levels.

6.24 Blood will be drawn at the time of surgery and sent for CA125 and a red top tube will be drawn and sent to the laboratory for 2,6, DMBQ testing

6.25 2,6-DMBQ determination

2,6-DMBQ will be determined in human plasma by high-performance liquid chromatography tandem mass spectrometry. The method will be validated per ICH/FDA guidelines and chromatography will be conducted similarly as previously published [20]. Plasma samples will be prepared for chromatographic injections by solid-supported liquid extraction (SLE). Calibration and quality control (QC) samples will be made by adding known amounts of 2,6-DMBQ to blank plasma. All calibration, QC, and unknown patient samples will be prepared in 96 well-plate format. Aliquots of human plasma and an internal standard will be added to a Biotage Isolute ® SLE plate. A non-polar solvent, similar to the previously published method, will be used to extract and elute the 2,6-DMBQ to a collection plate. The eluate will be evaporated under a gentle stream of air and wells will be reconstituted with mobile phase for injection. Samples will be injected into a Thermo Accela/TSQ Quantum LC/MS/MS system (Thermo Scientific, San Jose, CA). Analytes will be separated using a C18 column. Column eluate will enter the mass spectrometer via electrospray ionization and

multiple reactions monitoring (MRM) will be employed for identification and quantitation. Peaks will be detected and integrated utilizing Thermo LC Quan software. Calibration curves will be generated for each run and patient sample concentrations back-calculated from the corresponding regression line.

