7. TREATMENT MODIFICATIONS

- 7.1 It is expected that the dose of FWGE used in this study will be well tolerated; therefore there will be no dose modification. Specimens will be collected from all patients who undergo surgery even if they do not complete the full course of medication.
- 7.2 Criteria for removal from study:
 - 7.31 Patient refusal to continue treatment.
 - 7.32 Patient non-adherence to study plan.
 - 7.33 Pregnancy
 - 7.34 Patient does not have surgery within 2 months of starting FWGE or placebo.
 - 7.35 Grade 3 or 4 allergic reaction to FWGE or placebo

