8. STUDY PARAMETERS & SERIAL OBSERVATIONS

The patient will be evaluated at the time of enrollment. Quality of life and toxicity will be monitored weekly. The final assessment will occur on the day of surgery. No further surveillance will be performed for this trial.

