8.1 Observations and Tests

The following observations and tests are to be performed and recorded:

	Baseline	Weekly	On the day of
	Daseille	Weekly	surgery
History & Physical Exam	Х		Х
Performance Status	Х		Х
WBC, Diff, Hgb, Hct, Platelets	Х		Х
Chemistries: Na, K, Cl, CO2,			
BUN, creatinine, glucose,	х		X
bilirubin(T/D), SGOT (AST),		^	
SGPT (ALT), Alk Phos,			
CA-125	Х		Х
2,6 DMBQ			1
Toxicity Assessment	2	2	2
Grade 1-4 AEs		2	2
QoL Survey	3	3	3
Cancer tissue for paraffin			Х
embedded and frozen			Α

- 1. drawn in a red top tube
- 2. National Cancer Institute's Common Toxicity Criteria CTC version 4
- 3. Quality of Life Survey (QoL) FACT-O

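### A woman removed before her preoperative bloods has no scheduled post-baseline blood count and, unless an unclear table mark is a weekly X, no metabolic panel

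*Combined protocol and SAP*

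**What the plan says.** Section 6.212 sets two times for the safety laboratory tests: "complete blood count, differential, comprehensive metabolic panel and CA125 test prior to starting protocol therapy and preoperatively". In the section 8.1 table the row "WBC, Diff, Hgb, Hct, Platelets" is marked at baseline and on the day of surgery, and its weekly cell is empty. The chemistry row, which includes "bilirubin(T/D), SGOT (AST", has the same two marks plus a character in the weekly position that this text does not resolve.

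Toxicity grading is more frequent. Section 6.214 requires it for "all grades at the time of enrollment, then weekly and the day of surgery". Section 8 names only quality of life and toxicity as weekly items. It then states: "The final assessment will occur on the day of surgery", and provides for no surveillance beyond that.

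The plan expects some women to leave without an operation. Under 6.22 a delayed patient may stay on product for up to 2 months, and then: "If surgery has not occurred after this 2-month period, the patient will be removed from the study". Section 7.34 repeats this as a removal criterion: "Patient does not have surgery within 2 months of starting FWGE or placebo". Other routes in 7.2 include "Patient refusal to continue treatment" (7.31), non-adherence, pregnancy and a severe allergic reaction. None of them comes with a laboratory test at removal, and no early-termination visit appears elsewhere in the plan.

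**The concern.** The second safety draw is tied to the operation rather than to the end of exposure. A woman who takes product and is removed before any preoperative draw contributes a baseline sample and nothing after it.

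This touches the primary objective (2.21), which covers safety and toxicity, graded by CTCAE v4.0 (11.1). The plan itself links CTCAE grades to laboratory values: neutrophils in 4.141, creatinine in 4.142, and bilirubin, SGOT and alkaline phosphatase in 4.143. It admits women already at grade 1 on these items. A weekly interview cannot grade a change in such items without a sample, and a baseline sample alone cannot show one. What goes unobserved is laboratory change without symptoms, possibly in a woman with as long an exposure as anyone in the trial.

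**Working it through.** **1. Scheduled observations, set side by side.** Take a delayed woman on product for the full 2 months (taken as 60 days). Sources: 6.212, 6.214, 6.22, 8 and 8.1.

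| Item | Has surgery | Removed, no preoperative draw |
|---|---|---|
| Baseline blood count | 1 | 1 |
| Post-baseline blood count | 1 | 0 |
| Weekly toxicity gradings | 8 | 8 |

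The gradings are 60/7 = 8.57, so 8 complete weeks. The post-baseline metabolic panel follows the blood count (1 against 0) if the unclear mark is not a weekly X. If it is a weekly X, each woman also has a panel for each completed week, and only the blood count is missing.

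**2. Exposure.** Planned maximum 4 weeks = 28 days; permitted maximum about 60 days. Ratio 60/28 = 2.14.

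**3. The plan's own loss figure.** Section 12.5 expects under 10% of 20 women to be lost for any reason, leaving 18 evaluable: 20 × (1 − 0.10) = 18, which reproduces. Read strictly, under 10% of 20 means at most 1 woman; the 18 evaluable allow for 2. This is an all-cause allowance. The plan gives no count for women removed before a preoperative draw.

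**4. Number affected (assumption: k = 0, 1 or 2).** This range matches the allowance in step 3. The worst case for one arm puts all k in the same group of 10.

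| k | Share of 20 | Women with a post-baseline count | Left in the arm, if all k fall there | Share of that arm missing |
|---|---|---|---|---|
| 0 | 0% | 20 | 10 | 0% |
| 1 | 5% | 19 | 9 | 10% |
| 2 | 10% | 18 | 8 | 20% |

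**5. What this does to a safety statement in one arm.** If no laboratory event is seen in n women, the exact one-sided 95% upper bound on the event rate is 1 − 0.05^(1/n). The chance of seeing at least one event at a true rate of 20% (an illustrative value, not from the plan) is 1 − 0.8^n.

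| n | Upper bound, zero events | Chance of at least one event |
|---|---|---|
| 10 | 25.9% | 89.3% |
| 9 | 28.3% | 86.6% |
| 8 | 31.2% | 83.2% |

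**The case against.** The strongest reply is that the gap is narrow and much of the ground is covered.

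- **Preoperative bloods can precede a cancelled operation.** Section 6.212 applies to all subjects and does not require that surgery follow. A woman delayed to 2 months may already have been sampled. This stands, and it confines the point to women who never reach that draw.
- **Other safety collection continues.** Weekly all-grade assessment runs while she is on study, serious events are reported and followed under 11.2, and clinical care may supply unscheduled values. This also stands, and leaves only symptomless laboratory change. None of it schedules a blood count.
- **Section 7.1 collects specimens after an incomplete course.** It does so only for women who undergo surgery, so it does not help here.
- **The metabolic panel turns on a mark lost in the PDF reading.** This is correct, and the panel is therefore stated conditionally. Neither 6.212 nor section 8 mentions weekly chemistry, but only the original page can settle it. The blood count does not depend on it.
- **The exposure ratio and the eight gradings describe any delayed woman.** A woman operated on at day 60 has both as well. The true difference is one draw per affected woman.
- **This is an unpowered pilot that already allows for some loss.** The disclaimer in 12.1 limits the conclusions that can be drawn, and 12.5 anticipates loss of this order. Neither says that an exposed woman needs no safety sample, and safety is what the pilot sets out to describe.

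**Conclusion.** The concern holds. Following the plan as written, a woman who takes product and is removed before a preoperative draw has no scheduled blood count after baseline. Whether she also lacks a metabolic panel depends on the unreadable mark.

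The consequence is minor. The number affected is unknown, probably small and possibly zero; the range of 0 to 2 of 20 is an assumption that matches the plan's all-cause allowance. In the worst case considered, with both women in one arm, 8 of 10 keep a value and the zero-event upper bound moves from 25.9% to 31.2%. The direction between arms is unknown, and no planned test changes. The point is worth acting on because it concerns the primary objective and costs very little to correct.

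**What to change.** In 6.212, 7.2 and the 8.1 table, define the second blood count and metabolic panel as an *end of study product* sample. Draw it preoperatively if surgery takes place; otherwise draw it when product stops or at removal from study, where the woman agrees. In the report, state for each arm how many women have a post-baseline value, so that any remaining gap is visible.

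Women who have surgery need no extra draw. The few who do not need one routine blood draw. Recovery will be partial, because women removed for refusal or non-adherence (7.31, 7.32) may decline or not attend.

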12.0 STATISTICAL CONSIDERATIONS

12.1 Study Design: This study is a randomized, double-blind, placebo-controlled, trial of the effect of FWGE on women with epithelial ovarian cancer scheduled to undergo surgery. As noted above, we recognize that the sample size in the current study will prohibit definitive statistical conclusions to be drawn on our primary objective (to test the safety and tolerability of FWGE), or our secondary objectives (to compare levels of FWGE active product, CA125 levels, proliferation, and gene expression in OVCAs from subjects receiving FWGE versus placebo). The study is neither designed nor powered to develop statistically significant results, rather, we seek to develop preliminary/pilot data that will enable us to pursue a future large phase II, peer-reviewed grant-funded

trial of adjuvant FWGE in women undergoing therapy for ovarian cancer. Preliminary data developed in the current proposal will support such grant applications.

- 12.2 Primary outcome variable: The principal parameters to be collected, analyzed and reported will be:
- patient and disease characteristics: age, race, co-morbidities, cancer histologic
 type and stage. Optimal versus suboptimal surgical cytoreduction.
 - differences in toxicity
 - differences in quality of life

For each measure, Student's t-test will be used to identify differences between FWGE-versus placebo-treated OVCAs.

- 12.3 Secondary outcome variables for placebo versus FWGE:
- -the presence of 2,6-dimethoxy-p-benzoquinone in the serum
- -the change in the tumor marker CA125,
- -tumor proliferation as measured by Ki-67.

For each measure, Student's t-test will be used to identify differences between FWGEversus placebo-treated OVCAs.

12.4 Secondary outcome variables for genomic changes in ovarian cancer tissue for placebo versus FWGE.

Expression values will be calculated using the robust multi-array average (RMA) algorithm implemented in the Bioconductor (http://www.bioconductor.org) extensions to the R statistical programming environment.

Student's t-test will be used to identify differentially expressed genes in comparisons between FWGE- versus placebo-treated genomic data. Differentially expressed genes will analyzed using GeneGO MetaCore™ software to identify represented biologic pathways.

12.5 Accrual, Sample Size, and Study Duration: The study plan is a one-stage, randomized, double-blind, clinical trial. Patients will be randomized with equal

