probability to receive either FWGE or placebo. The study will accrue 20 patients. It is anticipated that the accrual of this many patients will be achieved in 18 months. Less than 10% of the patients registered are expected to be lost due to follow-up or any other reason, so 20 accruals should allow for 18 evaluable cases.

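### If the arrays fall into more than one batch with arms unevenly spread, ComBat (6.233) followed by a plain t-test (12.4) shrinks the FWGE effect or makes p-values too small; the two sections also need reconciling

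*Combined protocol and SAP*

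**What the plan says.** Section 6.233 describes the array work. The material is fixed in number: "A total of 20 fresh frozen primary OVCA tissues (10 FWGE- and 10 placebo-treated) will be used for RNA extraction". Values are normalised by IRON, and then: "Batch effects will be checked by using PCA; if present, they will be removed using COMBAT [19". Filtering follows: "The 54,675 probesets will be screened to remove control probesets, probesets with a small variance, and probesets expressed at low levels". The section does not say what constitutes a batch, what PCA finding would count as a batch effect, or whether treatment arm is kept as a covariate when ComBat is run.

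Section 12.4 gives the test: "Student's t-test will be used to identify differentially expressed genes in comparisons between FWGE- versus placebo-treated genomic data". It has no batch term, computes expression values by RMA rather than IRON, and does not mention ComBat. The selected genes go on to pathway analysis.

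On allocation, section 5.4 (Drug Dispensing) says: "A random number table will be used to assign patients to the FWGE versus placebo group". The pharmacy keeps the key until the study is complete. Section 12.5 gives equal allocation of 20 patients and says of accrual: "It is anticipated that the accrual of this many patients will be achieved in 18 months". No section links allocation to the extraction or hybridisation runs.

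**The concern.** Read together, the two sections correct for batch in one step and test arm in a second step that treats the corrected values as raw data. There are two ways to run the first step.

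- **ComBat without arm.** Each batch is centred on its own mean. If one batch holds more FWGE tumours than the other, part of the FWGE difference sits in the batch means and is removed with them.
- **ComBat with arm.** The arm difference is preserved, but the t-test does not know that batch was estimated from the same 20 arrays. Its standard error is too small and it has too many degrees of freedom. A slight excess of small p-values remains even when the arms are balanced.

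At stake is the gene list sent to pathway analysis, which is part of the preliminary data for the planned phase II application. This is separate from the choice between IRON and RMA and from multiplicity control; settling either would leave it in place.

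**Working it through.** **The plan's own figure.** Section 12.5 expects under 10% loss: 20 × (1 − 0.10) = 18, which agrees with "so 20 accruals should allow for 18 evaluable cases". That figure is not in dispute. The plan gives no figure for batch, so what follows is an illustration.

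**Inputs from the plan.** 20 arrays, 10 per arm (6.233); Student's t-test without a batch term (12.4).

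**Assumptions.** Two batches of 10, formed without regard to arm; batch acts as a location shift only; two-sided 0.05 per gene.

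**Chance of imbalance.** The number of FWGE tumours in the first batch is hypergeometric (20 tumours, 10 FWGE, 10 drawn). A split of 6:4 or worse in either direction has probability 0.656, 7:3 or worse 0.179, and 8:2 or worse 0.023.

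**Size of the distortion.** With *k* FWGE tumours in the first batch, the batch-arm correlation is r = (2k − 10)/10.

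- Without arm, the share of the effect kept is 1 − r².
- With arm, the adjusted arm difference equals the estimate from the arm + batch model. Its proper variance is larger than the t-test assumes by 1/(1 − r²), and its residual variance has 17 degrees of freedom, not 18. The t-test's critical value is 2.101 on 18 df. Its true type I error is therefore P(|T₁₇| > 2.101 × √[(1 − r²) × 17/18]).

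| Split | r | Effect kept, no arm | Type I error, with arm |
|---|---|---|---|
| 5:5 | 0 | 100% | 5.7% |
| 6:4 | 0.2 | 96% | 6.2% |
| 7:3 | 0.4 | 84% | 7.9% |
| 8:2 | 0.6 | 64% | 12.1% |

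Location-shift simulations agree: with arm, 7.6% to 7.8% at 7:3 and 11.9% to 12.1% at 8:2. Without arm, type I error falls below 5% (about 3.5% at 7:3 and 1.4% at 8:2), so that branch loses true effects rather than adding false ones.

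**Average over random splits.** The hypergeometric variance of k is 10 × 0.5 × 0.5 × 10/19 = 1.316, so the mean of r² is 4 × 1.316/100 = 0.053. On average 94.7% of the effect is kept without arm. Averaging the type I error formula over the same splits gives about 6.4% with arm.

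**Full empirical-Bayes ComBat.** This simulation used 20,000 genes and 8 runs, with 10% of genes shifted by 1 SD and a batch-shift SD equal to the within-gene SD (all assumed).

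| Split | Effect kept, ComBat no arm | Type I, ComBat with arm | Type I, arm + batch model | Type I, batch ignored |
|---|---|---|---|---|
| 5:5 | 95% | 6.7% | 5.0% | 2.7% |
| 6:4 | 92% | 7.1% | 4.9% | 3.8% |
| 7:3 | 82% | 9.0% | 5.1% | 10.1% |
| 8:2 | 66% | 12.8% | 5.0% | 25.8% |

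The last column is what follows if 12.4 alone governs and batch is not handled. The arm + batch model recovers 0.99 to 1.00 of a true effect of 1.0 at every split.

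**The case against.** The strongest reply is that nothing in the documents says there will be more than one batch. ComBat is conditional on a batch effect being found. The tumours are flash frozen, and all 20 could go through in one run at the end. The 18-month figure concerns enrolment, not array scheduling. This stands: the plan is silent on layout, and the harm in this trial cannot be sized.

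It also stands that the commonest imbalance, 6:4, does little harm, and that the striking 8:2 figures belong to 2.3% of random splits. A reader might infer that the gene list will be seriously distorted, or that about a third of the effect would typically be lost. The documents support neither.

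A third reply is that 12.4 sets no significance level or false discovery rate, and that unadjusted testing of up to 54,675 probesets (before filtering) outweighs a rise from 5% to 6–8% per gene. That is fair as to priority. But multiplicity control would not cure the fault: in the full ComBat simulation with arm, Benjamini-Hochberg at 5% gave 53 false genes among 289 selected at 7:3 (18%) and 200 among 574 at 8:2 (35%).

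Finally, the ComBat-then-t-test sequence is assembled from two sections that disagree on normalisation. This is correct. It is a reason to reconcile them, and neither reading puts batch into the test.

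**Conclusion.** The point holds in conditional form. As written, the plan either adjusts for batch and then tests as if it had not (6.233 with 12.4), or does not handle batch at all (12.4 alone). With more than one batch and uneven arms, the first reading shrinks the FWGE effect or makes p-values too small, depending on how ComBat is run. With arm in ComBat there is mild inflation even at a 5:5 split (5.7% by formula, 6.7% with full ComBat).

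Under the two-batch assumption the usual distortion is small, and it becomes material from about 7:3, an 18% chance. The number and size of batches, random batch formation and the size of the batch shift are all assumptions.

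Some might read this as a threat to the trial's main conclusions. It is not: safety, toxicity and quality of life do not depend on the arrays, and the plan says the pilot is not powered for significance. It is a worthwhile improvement to a secondary, exploratory analysis, not a necessary correction.

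**What to change.** In 6.233 and 12.4:

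1. State one pipeline, with a single normalisation method and a single statement on batch, in both sections.
2. Where feasible, extract, label and hybridise all frozen tumours together after the last surgery, in an arm-balanced coded order supplied by the pharmacy, so that the laboratory stays blinded.
3. If more than one batch is needed, balance arms over batches in the same way and record the batch of each array.
4. In that case, test arm in one per-gene linear model with terms for arm and batch (for example a moderated t-test), on data not adjusted by ComBat. Keep PCA and ComBat output for plots.

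**Cost.** Changes of wording and laboratory scheduling. Array data wait until accrual ends, although the arm key is withheld from the researchers until the study is complete in any case. Each extra batch costs one degree of freedom. If imbalance remains, the model shows its price openly: in the simulation, power for a 1 SD shift was 0.56 at 5:5, 0.49 at 7:3 and 0.40 at 8:2.
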